The advantages of fast-track principles that have been documented in connection with abdominal surgery most likely extend to the field of gynecology, but this is only an assumption, since fast-track in elective gynecological surgery has not been studied carefully so far. There is an existing research showed FTS in gynecological oncology provide early hospital discharge after gynaecological surgery meanwhile with high levels of patient satisfaction [10]. However, no consensus guideline has been developed for gynecological oncology surgery although surgeons have attempted to introduce slightly modified FTS programmes for patients undergoing such

surgery .NO randomised controlled trials for now[3, 11, 12].

In contemporary surgical care patients would often be admitted to hospital the day prior to planned surgery, undergo preoperative mechanical and antibiotic bowel preparation and have IV fluids running to keep them in fluid balance, prior to any surgical or anaesthetic insult. Intraoperatively patients were often volume loaded to maintain a filling pressure, as well as pelvic drains to prevent development of collections, then spent 2 - 3 days nil by mouth (NBM) until bowel sounds were heard before being commenced on a graduated diet of clear liquids, free fluids, light diet and finally commenced on a regular diet 5 - 7 days post surgery. Patients were then discharged, on average 5 - 7 days post surgery[13]. Fast Track Surgery (FTS) or Enhanced Surgical Recovery (ESR) programs have been developed and refined in many specialties with documented improved patient outcomes and as a consequence earlier discharge from hospital and reduced length of stay (LOS)[2, 14, 15].

The aim of this study is to identify patients following a FTS program who have been discharged earlier than anticipated after major gynaecological/gynaecological oncologic surgery and analyze the complication after surgery.

Methods/Design

Objectives and hypothesis

Comparison of Fast-Track (FT) and traditional management protocols.

The following hypotheses will be tested:

H0: The recovery and postoperative complications is equal in both groups.

H1: The recovery was enhanced and postoperative complications is different in both groups.

Study population and eligibility criteria

The trial is designed as a randomized, controlled, nonblinded and single-center trial.

The centre: Department of gynecological oncology of Si Chuan Cancer Hospital Chengdu, Sichuan, China

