Detailed inclusion and exclusion criteria are described below.

Inclusion criteria

1. Patients scheduled for gynecological oncology surgery (including radical hysterectomy add lymphadenectomy, hysterectomy add lymphadenectomy and cytoreductive).
2. Aged 18 years or older
3. Signed informed consent provided

Exclusion criteria

1. Patients with a documented infection at the time of operation.
2. Aged 71 years or older.
3. Patients with ileus at the time of operation.
4. Patients with hypocoagulability.
5. Patients with psychosis, Alcohol dependence or drug abuse history;

6. Patients with primary nephrotic or hepatic disease;
7. Patients with severe hypertension systolic pressure ≥ 160 mmHg, diastolic pressure > 90 mmHg.

Sample size calculation

The sample size calculation is based on the Length of hospitalization post-operation. The standard deviation of length of hospitalization post-operation in the traditional group is 1.5 based on previous studies [16, 17].

We estimated the number of patients needed in a superiority trial with an effect size of 90 % and a margin of 10 (alpha 5 %, power 90 %). where $u_{\alpha} = 1.96$ and $u_{\beta} = 1.28$ and using the equation $n = [2(u_{\alpha} + u_{\beta}) \sigma / \delta]^2$, a sample size of 47 patients per group is necessary to detect a difference between the groups. With an expected dropout rate of 20%, we plan to enrol 120 patients into the study.

Postoperative data collection

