A daily visit of the study patients will be made by clinical investigators or a delegated physician. All protocol-required information collected during the trial will be entered into the patient's record form. Data collected relate to 1) patient characteristics, 2) hospitalisation 3) post-operation and 4) complications. The patient characteristics collected were: age, weight, height, body mass index (BMI), medical insurance status and performance status. Hospitalization details included LOS (Length of hospitalization post-operation), the procedure performed, diagnosis, operating time, name of surgery, intraoperative estimated blood loss. Post-operation details included time to full tolerance of free fluids (days), time to full tolerance of solid food (days), time to drain removal (days). Complications details included infection (wound infection, lung infection, intraperitoneal infection, operation space infection), postoperative nausea and vomiting (PONV), ileus, postoperative hemorrhage, postoperative thrombosis and APACHE II score. (Table 1).

Primary and secondary endpoints

Primary endpoints

Length of hospitalization post-operation (d, mean \pm SD). It was calculated by the difference between date of discharge and date of surgery.

Secondary endpoints

Complications: complications in both groups are assessed during the first 21 days postoperatively. Including infection (wound infection, lung infection, intraperitoneal infection, operation space infection), postoperative nausea and vomiting (PONV), ileus, postoperative hemorrhage, postoperative thrombosis and APACHE II score. (Table 1).

Ethics, study registration and consent

This trial was approved by independent ethics committees at Sichuan Cancer Hospital and Research Institute

Board Affiliation: SichuanCHRI

[contact] Email: [contact]

The study procedures, risks, benefits and data management will be clarified with the patients before they are asked to give their informed consent to participate.

Study treatment

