and containing a sheet that states the group allocation for the patient. Randomization envelopes will be used in consecutive order. Basic characteristics of the patient and the day of randomization will be documented on a data sheet so that compliance to the randomization scheme may be checked retrospectively. If patients are excluded from the study after randomization, their numbers will not be reused. Obviously, operating surgeons, attending physicians and nursing staff and the patients and families cannot be blinded, as the procedure is different. However, outcome assessors will be blinded. The randomization process will follow the CONSORT guidelines (Figure 1)[21].

Minimizing treatment bias

gynecological oncology surgery (including radical hysterectomy add lymphadenectomy, hysterectomy add lymphadenectomy and cytoreductive) are standardized in both group, all surgeons participating in the study are familiar with them. common procedure performed on a routine basis, which eliminates a learning curve.

Minimizing measurement bias

Detection an length of hospitalization post-operation and postoperative complications, which are the primary and secondary endpoints, will be based on data in the patient's record form. Blinding is not necessary, because the length of hospitalization post-operation is an objective endpoint that cannot be influenced by the patient. Physician blinding is not possible, because they are involved during surgery.

Statistical methods

Each patient's allocation to the analysed population will be defined prior to the analysis and will be documented. In the full-analysis set, patients will be analysed as randomized according to the intention-to-treat principle. The intention-to-treat principle implies that the analysis includes all randomized patients. The per-protocol analysis set will include all the patients without major protocol deviation. Deviations from the protocol will be assessed as major or minor. Patients with major deviations from the protocol will be excluded from the per-protocol analysis. The safety analysis set will analyse patients according to the treatment.

The null hypothesis assumes that the length of hospitalization post-operation and postoperative complications is equal in both groups. A binary logistic regression will be applied in order to compare length of hospitalization post-operation in the groups adjusting for other factors.

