Data were analyzed by SPSS19.0 (SPSS Inc Chicago, Illinois) and expressed as mean \pm SD. Length of hospitalization post-operation in the FTS and traditional groups were compared and analyzed by Mann-Whitney U-tests (non-normal distribution).

NRS2002 scores between the two groups were analyzed with the Wilcoxon test (nonnormal distribution) or with Student's t-tests (normal distribution). The chi-square test or Fisher's exact test will be used for analysis of categorical secondary endpoints (complications). A P-value <0.05 will be considered statistically significant. Statistical analyses will be performed using SPSS19.0 (SPSS Inc Chicago,

Illinois).

Discussion

Fast-track surgery (FTS) pathway have been adopted by most surgical specialties worldwide, but in gynecological malignant surgery is sparingly described[22] and there are currently no randomized controlled trials to support or refute employing this approach[11]. This needs to be explored right now.

However, no consensus guideline has been developed for gynecological oncology surgery although surgeons have attempted to introduce slightly modified FTS programmes for patients undergoing such surgery .NO randomised controlled trials for now[3, 11, 12].

Widespread education is needed to improve the rate of implementation of fast-track. There are several possible reasons for this, including lack of collaboration in the surgical team and lack of awareness of or failure to accept and adopt evidence-based findings[8, 9, 23]. Close cooperation between the surgical, anesthesiological and nursing staff is essential and the importance of cooperation cannot be overestimated as practice needed to achieve further development of surgical care and postoperative recovery[24, 25]. Fast-track regimens in general have been well evaluated regarding medical complications and they appear to be safe[26].

The aim of this study is to compare the LOS(Length of hospitalization post-operation) after the major gynaecological/gynaecological oncologic surgery and analyze the complication after surgery. This trial can show whether the FTS program can achieve early hospital discharge after gynaecological surgery meanwhile with low levels of complications.

Trial status

At the time of writing, we are about to enroll patients and the anticipated study completion date is April 2017.

Abbreviations

Abbreviations	Definition
FTS	Fast-track surgery
LOS	Length of hospitalization post-operation
PONY	postoperative nauseaand vomiting

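### Complications are to be compared by significance test alone, with no effect estimate or confidence interval, so the plan cannot answer its own question about complication levels

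*Combined protocol and SAP*

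**What the plan says.** Complications are the named secondary endpoint. Under Primary and secondary endpoints, "complications in both groups are assessed during the first 21 days postoperatively". The list covers infection (four types), nausea and vomiting, and "ileus, postoperative hemorrhage, postoperative thrombosis and APACHE II score".

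Complications are also part of the formal hypotheses. Objectives and hypothesis has "H0: The recovery and postoperative complications is equal in both groups", and Statistical methods repeats that "The null hypothesis assumes that the length of hospitalization post-operation and postoperative complications is equal in both groups".

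The analysis is given in two sentences of Statistical methods: "The chi-square test or Fisher's exact test will be used for analysis of categorical secondary endpoints (complications") and "A P-value <0.05 will be considered statistically significant".

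The Abstract and the main Discussion both state what the trial is expected to deliver: "This trial can show whether the FTS program can achieve early hospital discharge after gynaecological surgery meanwhile with low levels of complications". No threshold is given for what counts as low.

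On size, the Sample size calculation section says "The sample size calculation is based on the Length of hospitalization post-operation".

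**The concern.** The question posed is how high complication rates are under fast-track care and how they compare with traditional care. The method named answers only whether the data contradict exact equality. With arms sized for a different endpoint, failure to contradict equality is weak evidence.

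Nothing else in the documents fills the gap. The only summary statistic named is mean ± SD, which does not describe yes/no events. The only model named, a binary logistic regression, would produce odds ratios, but the text assigns it to length of stay. A safety analysis set is defined, but no estimate is attached to it.

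A reader given only a P-value could not tell similar rates from too few patients to know. This matters because the plan itself says that no randomised trials exist in this field, so readers would lean on this comparison.

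**Working it through.** **The plan's own figures.** There is none for complications to reproduce. The 47 per group concerns length of stay. With the stated SD of 1.5, the stated 1.96 and 1.28, and an assumed difference of 1 day (the plan gives none), 2 × (3.24 × 1.5 / 1)² = 47.2 per group. No complication rate enters that sum.

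**Inputs.**
- Patients per arm: 120 enrolled / 2 = 60, assuming equal arms. As a sensitivity case, 60 × 0.8 = 48 if the expected 20% dropouts contribute no complication data.
- Significance rule: P<0.05, taken as two-sided in line with the 1.96.
- Complication rates: not in the documents. Baselines of 5%, 10% and 20% are assumptions. So are 25% and 30%, added because Table 2 describes nausea and vomiting as common. The true effect is assumed to be a doubling.

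**Step 1: chance of missing a doubling.** Exact power is the sum, over all pairs of counts (x, y), of Bin(x; n, p) × Bin(y; n, 2p), counting only pairs with P<0.05. Missed = 1 - power. Chi-square is without continuity correction.

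| Rates | Power, n=60: chi-square / Fisher | Missed, n=60 | Power, n=48: chi-square / Fisher | Missed, n=48 |
|---|---|---|---|---|
| 5% v 10% | 0.174 / 0.088 | 83-91% | 0.171 / 0.058 | 83-94% |
| 10% v 20% | 0.326 / 0.247 | 67-75% | 0.293 / 0.182 | 71-82% |
| 20% v 40% | 0.684 / 0.600 | 32-40% | 0.586 / 0.490 | 41-51% |
| 25% v 50% | 0.818 / 0.760 | 18-24% | 0.725 / 0.643 | about 28-36% |
| 30% v 60% | 0.924 / 0.894 | 8-11% | 0.854 / 0.801 | 15-20% |

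**Step 2: how large a difference must be seen.** Against 6/60 in one arm, P first falls below 0.05 at 15/60 in the other by chi-square and at 16/60 by Fisher. Those are rates of 25% and 27% against 10%.

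**Step 3: what the P-value hides.** Take 12/60 v 6/60, a difference of 0.20 - 0.10 = 0.10. Fisher P = 0.20 and chi-square P = 0.125. The Wilson 95% limits are 0.1183 to 0.3178 for 12/60 and 0.0466 to 0.2015 for 6/60. The Newcombe interval combines them:
- lower: 0.10 - √[(0.20 - 0.1183)² + (0.2015 - 0.10)²] = 0.10 - 0.130 = -0.030
- upper: 0.10 + √[(0.3178 - 0.20)² + (0.10 - 0.0466)²] = 0.10 + 0.129 = +0.229

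The data would fit anything from 3 points fewer to 23 points more.

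**Step 4: equal counts.** By the same method at 60 per arm, 3 v 3 gives ±9.3 points, 6 v 6 gives ±11.5 and 12 v 12 gives ±14.3. Fisher P is 1.00 each time.

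**The case against.** **Secondary endpoints are usually unpowered, and the plan makes no equivalence claim.** This stands. The alternative hypothesis is that complications differ, and the sentence about low levels says the trial can show whether this is so, which leaves the result open. A reader might infer that the investigators will treat P>0.05 as proof of safety, or that they promise low rates. The documents say neither. What remains is that the named analysis cannot settle the question raised.

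**The size of the problem rests on assumed rates.** This also stands. Across the assumptions the missed share runs from 94% down to 8%, and doublings from 25-30% are usually detected. The 48-per-arm case applies only if outcomes are missing, since the intention-to-treat analysis is said to include all randomised patients.

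**The logistic regression may have been meant for complications.** That is plausible, because it suits yes/no outcomes and follows directly after a null hypothesis that covers both endpoints. As written it is for length of stay, so it does not supply the estimate.

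**Intervals could be added at the reporting stage.** They could, from the same counts. Stating them beforehand fixes what the conclusion will rest on, and the plan says enrolment was only about to start.

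**APACHE II.** A reader might go further and infer that earlier discharge would leave these scores missing more often in one arm. The documents do not show this: the 5-7 day discharge figure is background on conventional surgical care, and no discharge time is given for this centre or the fast-track arm.

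**Conclusion.** The concern holds as a gap in the analysis of complications. It does not affect the length-of-stay comparison, the sample size or the data to be collected. The omission itself is certain from the text.

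Its consequence depends on event rates that the documents do not give. If a complication occurs in about 5-10% of patients, a real doubling would go undetected in at least two trials in three at 60 per arm. At 20% the miss rate is roughly a third or more. For common events such as nausea and vomiting the tests are reasonably adequate. These figures assume equal arms, two-sided testing and complete outcome data.

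The change is worth making before analysis. It is not a reason to doubt the trial's primary result.

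**What to change.** In Statistical methods, add wording along these lines:

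*Each yes/no complication will be reported as n/N (%) per arm with the risk difference (FTS minus traditional) and a 95% confidence interval suited to small counts (for example Newcombe), in the full-analysis set and repeated in the safety analysis set. Chi-square or Fisher's exact tests are supporting. Statements about complications will rest on the intervals; a P-value above 0.05 will not be taken as evidence of similar rates. These comparisons are secondary and the trial was not powered for them.*

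If the logistic regression was intended for complications, the plan should say so.

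As a side note, the categorical tests do not fit the numeric APACHE II score, so name a Wilcoxon rank-sum test for it.

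**Cost.** One interval per complication, from counts already planned: five with infection as one item (infection, nausea and vomiting, ileus, haemorrhage, thrombosis), or eight with its four types separate. No extra patients or visits are needed. The interval may need a short hand calculation or a macro if the named software does not produce it. Intervals add no power. For the less common events they will probably still include sizeable increases, so the conclusion on safety will be more cautious.

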Parameters	Definitions
patient characteristics	age, weight, height, body mass index (BMI), medical insurance status and per-formance status.
hospitalisation	LOS(Length of hospitalization post-operation), the procedure performed, diagnosis, operating time, name of surgery, intraoperative estimated blood loss
Post-operation	time to full tolerance of free fluids (days), time to full tolerance of solid food (days), time to drain removal (days).
Complications	
infection	wound infection, lung infection, intraperitoneal infection, operation space infection
postoperative nausea and vomiting (PONV)	it was recognized that nausea and vomiting are common side effects of surgical recovery
Ileus	is a disruption of the normal propulsive ability of the gastrointestinal tract
Postoperative haemorrhage	Evidence of blood loss from drains or based on ultrasonography

Postoperative thrombosis	Evidence of blood thrombosis based on ultrasonography
APACHE II score	Acute Physiology and Chronic Health Evaluation II

Figure1 Study flow diagram

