The surgical technique is standardized in The treatment team and the patients' families were not blinded to the study. In addition, the data collectors were not involved in the clinical management of patients to ensure statistical validity and reliability. All surgeries were performed by the same team of surgeons, and the patients were treated and nursed by the same treatment team during the peri-operative period. Post-operative complications were based on patient complaints and clinical symptoms.

Given there was no Fast-track surgery guideline in the field of gynecological oncology surgery , we refer to the guideline of gastrectomy, colorectal surgery and pancreaticoduodenectomy[18-20].(Table1)

Safety aspects

Gynecological oncology surgery is highly technically demanding procedure. In order to avoid bias based on the learning curve of the surgeons, every surgical procedure will be performed or supervised by a senior surgeon. And informed consent will be obtained from all participants,

Data collected relate to 1) patient characteristics, 2) hospitalisation 3) post-operation and 4)complications. The patient characteristics collected were: age, weight, height, body mass index (BMI), medical insurance status and per-formance status. Hospitalization details included LOS(Length of hospitalization post-operation), the procedure performed, diagnosis, operating time, name of surgery, intraoperative estimated blood loss. Post-operation details included time to full tolerance of free fluids (days), time to full tolerance of solid food (days), time to drain removal (days). Complications details included infection(wound infection, lung infection, intraperitoneal infection, operation space infection), ileus, postoperative hemorrhage, postoperative thrombosis and APACHE II score. (Table 2).

Methods for avoiding bias

Minimizing systemic bias

Patients will be randomized to one of the two groups after admitting diagnosis. Randomization will be accomplished using balanced permutation blocks by generation of random numbers in order to obtain homogeneity between groups. Opaque, sealed envelopes will be produced, labelled with the randomization number

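### Postoperative haemorrhage has no severity threshold and depends on drains, so it may over-count events, dilute a real difference or create a drain-related one

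*Combined protocol and SAP*

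**What the plan says.** Table 2, which lists the parameters and complications for analysis, contains the only definition of postoperative haemorrhage: "Evidence of blood loss from drains or based on ultrasonography". No volume, haemoglobin fall, transfusion, re-intervention or grade appears there or elsewhere. The Study treatment section gives another basis for all complications: "Post-operative complications were based on patient complaints and clinical symptoms". The Secondary endpoints section names haemorrhage among the complications and sets the window: "complications in both groups are assessed during the first 21 days postoperatively". That section refers to Table 1 for complications, but Table 1 holds perioperative management; the definitions are in Table 2.

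On drains, time to removal is a listed data item (Postoperative data collection, Safety aspects, Table 2). The Background mentions drains when describing contemporary care: "as well as pelvic drains to prevent development of collections". Table 1 does not mention drains for either arm.

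Categorical complications are compared by chi-square or Fisher's exact test (Statistical methods), and "A P-value <0.05 will be considered statistically significant". Under Minimizing systemic bias, the plan says that outcome assessors will be blinded. Under Minimizing measurement bias, it says that blinding is not needed because length of stay is objective.

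**The concern.** The definition is a stated rule, but it lacks the threshold that would separate a complication from expected drainage. The eligible operations include radical hysterectomy with lymphadenectomy and cytoreduction. If some blood in a drain is ordinary after these, a literal reading counts it as an event.

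Two distortions follow, in opposite directions. If drains are used alike in both arms, incidental events are added to both, and a true difference in bleeding is diluted. If drain use or duration differs by arm, the arm with more drain exposure has more chances to record an event, and a difference can appear without any difference in bleeding. In an open-label trial that treats drain removal time as a recovery measure, with no drain policy in Table 1, such a divergence is possible.

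The two rules can also disagree about one patient. A patient without symptoms who has blood in the drain is an event under Table 2 and not under the Study treatment sentence. At stake is the plan's stated aim, in its Discussion, of showing early discharge together with few complications.

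**Working it through.** **Inputs from the documents.** Total enrolment is 120, taken as 60 per arm because the blocks are balanced (the ratio is not stated). The sample size calculation requires 47 per group. The test is Fisher's exact at 0.05, taken as two-sided. The plan gives no event rate, effect size or power for haemorrhage, so there is no figure of its own to reproduce.

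**Assumed inputs.** These are the true haemorrhage rate p, the share of patients drained d, the chance q that a drain shows incidental blood, and the share f of non-events labelled as events. The documents give none of them.

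**Dilution (same f in both arms).** Observed rate = p + (1 − p)f. With p = 5% and 25% and f = 10%, the observed rates are 0.05 + 0.95 × 0.10 = 14.5% and 0.25 + 0.75 × 0.10 = 32.5%. Power is by exact binomial enumeration:

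| f | Observed rates | Power, 60 per arm | Power, 47 per arm |
|---|---|---|---|
| 0 | 5.0% vs 25.0% | 85% | 71% |
| 10% | 14.5% vs 32.5% | 57% | 45% |
| 50% | 52.5% vs 62.5% | 15% | 12% |
| 80% | 81.0% vs 85.0% | 5% | 4% |

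The true contrast is itself an assumption, so smaller ones are shown at 60 per arm:

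| True rates | f = 0 | f = 10% | f = 50% | f = 80% |
|---|---|---|---|---|
| 5% vs 20% | 63% | 35% | 10% | 4% |
| 5% vs 10% | 9% | 6% | 4% | 3% |

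At 5% versus 10% there is little power to lose, even with a perfect definition.

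**False difference (equal true rates).** Observed rate = p + (1 − p)dq. With p = 5% in both arms, d = 100% versus 50% and q = 50%:

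- Arm with all patients drained: 0.05 + 0.95 × 1.0 × 0.5 = 52.5%.
- Arm with half drained: 0.05 + 0.95 × 0.5 × 0.5 = 28.75%.
- Chance of a significant result: 70% at 60 per arm, 57% at 47 per arm.

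At 60 per arm, the same drain split gives 26% for q = 25% and 99% for q = 80%. A milder split of 100% versus 80% gives 6%, 14% and 39% for q = 25%, 50% and 80%. With equal drain use the figure is about 3% at each of these values of q.

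Only the product dq enters the formula, so a difference in duration acts in the same way. If all patients are drained but longer drainage raises q from 25% to 50%, the observed rates are again 28.75% and 52.5%.

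**The case against.** The strongest reply is that Table 2 does not say that any blood counts. The entry speaks of blood loss, under the name of a complication, and a clinician might well apply it only to abnormal bleeding. If the Study treatment sentence is read as an added condition, incidental blood in a well patient would not count. Both readings are possible, but the plan does not state either. This supports reconciling the passages; it does not show that the present wording is adequate.

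A reader might infer that most drained patients would be events, or that the endpoint could not tell the arms apart. The documents do not support either inference. They do not say what share of drains shows blood, and unequal drain use could produce a difference instead of hiding one. Nor do they say that every patient is drained: removal time is only a listed item, and the remark on pelvic drains is background on conventional care.

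A reader might also infer that unblinded staff will call the events. The plan states that outcome assessors are blinded and that data collectors are not involved in clinical management. Its later remark that blinding is unnecessary leaves this unclear, but does not establish the contrary. In any case, a blinded assessor has no threshold to apply.

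It is also fair to say that haemorrhage is one component of a secondary endpoint and that the trial was not sized for it. If haemorrhage is uncommon, low power comes mainly from the sample size. The false-difference mechanism remains.

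**Conclusion.** The point holds in a limited form. The haemorrhage rule has no severity threshold, is partly tied to drain presence and duration, and differs from the plan's other stated basis for complications. It may over-count events, dilute a real difference or create a drain-related one; the documents do not allow a choice between these or an estimate of their size. The illustrations run from almost no effect (5% versus 10%, where power is about 9% at best) to a fall in power from 85% to 5%, or a false-positive chance of about 70%. All rest on assumed true rates, drain use and frequency of blood in drains. The primary endpoint and its sample size are unaffected. The change should be made, because the rule is used for a tested safety comparison and the correction is small.

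**What to change.** In Table 2, count haemorrhage for analysis only when a bleeding consequence is recorded, such as transfusion, re-operation or another bleeding-related intervention, or a haematoma confirmed by imaging. Have the blinded outcome assessors whom the plan already names classify it in the same way in both arms. Report blood in drains descriptively, by arm, beside time to drain removal. Reconcile the Study treatment sentence with Table 2 so that one rule applies, and correct the table reference in the Secondary endpoints section.

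The cost is a short text change and perhaps one or two fields on the record form. Transfusion and re-operation are not among the listed data items, so it should not be assumed that they are already captured. The downside is fewer counted events in a trial not sized for this endpoint, so the result should be read as descriptive safety information as much as a test.
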